6 ANALYSIS POPULATIONS

6.1 Screened Population

The Screened Population will consist of all subjects who underwent at least one Screening Visit and received a subject identification number.

6.2 Full Analysis Set

The Full Analysis Set will consist of all enrolled subjects who received at least one dose of investigational product. Subjects will be analyzed according to randomized treatment sequence.

6.3 Per Protocol Set

The Per Protocol Set will consist of all subjects in the Full Analysis Set who meet the following criteria:

- The percentage of days with non-missing movement disorder diary is at least 80% for the planned run-in period duration (6 weeks) and each of the two planned maintenance period durations (8 weeks).
- The percentage of days with non-missing doses is at least 80% for each of the two planned maintenance period durations (8 weeks).
- After titration period, the target dose (25%) of UX007 is reached for at least one day for the planned maintenance periods.

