#### 7.4.4 Selection of Doses

The UX007 dose and regimen for this study was selected based on the extensive clinical information derived from over 15 years of clinical experience in a variety of diseases. Approximately 200 subjects have received triheptanoin treatment, 51 of which involved pediatric patients as young as neonates, with 23 of these 51 patients with over 5 years of treatment duration (Roe et al. 2002, Roe et al. 2006, Mochel et al. 2010).

UX007 (triheptanoin) is a liquid, intended for oral (PO) administration. UX007 is a colorless to yellow oil supplied in 1 L round, translucent high-density polyethylene (HDPE) or 1 L round amber colored glass bottles. Subjects will be dosed according to an age- and weight-based strategy (Table 7.4.4.1), up to a maximum daily administration of 130g. For subjects within 25% predicted BMI, actual body weight will be used to calculate the appropriate dose per the subject's age category. Adjusted body weight will be used for subjects with greater than 25% predicted BMI, to account for metabolic activity found in adipose tissue versus lean muscle. Adjusted body weight will be calculated in kilograms, using the following formula:

Formula 1# Adjusted Body Weight = Ideal Body Weight + [25% × (Actual Body Weight – Ideal Body Weight)]

UX007 dosing will be initiated using a 2-week titration schedule until the subject has reached his/her target total daily dose. If a subject has not reached the target total daily dose by the end of the 2-week titration period, dose titration should continue until the maximum tolerated dose is reached. For detailed information regarding dosing and titration, please refer to the Study Reference Manual.

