**Table 7.4.4.1: Age- based UX007 Target Total Daily Dose**

Age Ranges	UX007 dose (g/kg/day) that is estimated equivalent to 30% total caloric intake
6 - 9 Years	2.5
10 - 14 years	2
15 - 20 years	1.5
21 and Over	1.2

The total daily dose will be divided into 4 equal doses, mixed with food or drink (or formula, as appropriate), and administered PO or by gastronomy tube at breakfast, lunch, dinner, and before bed. The dose may be divided into smaller more frequent doses with food or drink as needed. The oil should not be taken without thoroughly mixing with food or drink. The dose should not be adjusted due to changes in age and/or weight during Treatment Periods 1 and 2.

The data support the safety of triheptanoin when administered at approximately 1-4 g/kg depending on age. Previous clinical data also suggest an age-dependent dose that relates to the relatively higher energy requirements for young children versus older children versus adults. The daily dose is consistent with prior clinical use in other diseases and is equivalent to approximately 2-4 g/kg in infants and young children, decreasing to 1-2 g/kg for older children, adolescents, and adults. Triheptanoin treatment has been generally safe and well tolerated at the aforementioned dose levels. Higher doses are poorly tolerated due to gastrointestinal disturbance, such as diarrhea; lower doses would likely provide suboptimal efficacy.

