8.6.2 Measurement of Treatment Compliance

Dosing compliance for a specified period is defined as the investigational product actually taken by a subject during that period in ml divided by the investigational product expected for the same period in ml multiplied by 100.

Descriptive statistics for dosing compliance will be summarized by treatment sequence and treatment for the Safety Analysis Set for the DB treatment and OLE Period. Number of days with non-missing dose will also be summarized by treatment sequence and treatment.

The percentage of subjects who reach target dose within 2 weeks of titration period will be summarized by treatment for the DB Treatment Period. Time to reach target dose will also be summarized by treatment.

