8.8.1 Analyses of Primary Efficacy Endpoint

The primary endpoint is the frequency of movement disorder events during the maintenance treatment period. In the event of electronic diary failure, the back-up paper diary might be used during the days with missing data from electronic diary. Combined electronic diary data and paper diary data will be used.

The primary analysis will be performed using a weighted ANCOVA model, with study baseline frequency of movement disorder as a covariate, treatment sequence, treatment group and period as fixed effects, and a random effect for subject within the sequence.

After study unblinding, the normality assumption of ANCOVA model will be examined by using the Wilk-Shapiro test on the residuals from the ANCOVA model (Shapiro et al. 1965). When there is strong evidence suggesting that the normality assumption is not met (p value for Wilk-Shapiro test < 0.05) (Normadiah 2011) (Yap et al. 2011), Wilcoxon rank-sum test will be considered as the primary analysis to assess treatment difference in movement disorder event frequency.

The following sensitivity analyses will be performed.

- To analyze the percent change from study baseline in the frequency of movement disorder during the maintenance period, the primary weighted ANCOVA model will be performed.
- Wilcoxon rank-sum test will be performed to assess treatment difference in movement disorder event frequency.
- The primary weighted ANCOVA based on the frequency of movement disorder events will be performed based on Per Protocol Set.
- In case paper diary is used as back up, sensitivity analysis excluding paper diary will be considered. The primary weighted ANCOVA based on the frequency of movement disorder events will be performed.
- If subjects discontinued during the 2-week titration period or missed one treatment period entirely, impute the movement disorder frequency during the maintenance period using the frequency during the titration period if titration period data is available, otherwise, the study baseline will be used to impute the movement disorder frequency during the maintenance period. Then the ANCOVA model based on the frequency of movement disorder events during maintenance phase will be performed, with study baseline frequency of movement disorder as a covariate, treatment sequence, treatment group and period as fixed effects, and a random effect for subject within the sequence.

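### The Per Protocol Set tests dosing by days with a recorded dose plus one day at an undefined target, not by the SAP's own volume-based compliance, so a subject at about 21–26% of expected volume can qualify

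*SAP*

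**What the plan says.** SAP 6.3 sets three criteria for the Per Protocol Set. The first concerns the symptom diary. The second and third concern dosing:

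- Second criterion: "The percentage of days with non-missing doses is at least 80% for each of the two planned maintenance period durations (8 weeks").
- Third criterion: "After titration period, the target dose (25%) of UX007 is reached for at least one day for the planned maintenance periods".

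SAP 8.6.2 measures adherence differently, as a ratio of volumes. Its numerator is the amount actually consumed, and its denominator is described only as "the investigational product expected for the same period in ml multiplied by 100". It lists the day count as a further, separate summary: "Number of days with non-missing dose will also be summarized by treatment sequence and treatment".

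The set is used in SAP 8.8.1, "The primary weighted ANCOVA based on the frequency of movement disorder events will be performed based on Per Protocol Set", and again in SAP 8.8.2 for total duration of events. Efficacy analyses otherwise use the Full Analysis Set (SAP 8.8).

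Two protocol statements bear on the dose criteria. Table 7.4.4.1 gives the target as a "UX007 dose (g/kg/day) that is estimated equivalent to 30% total caloric intake". Section 7.4.4 foresees subjects below target, for whom "dose titration should continue until the maximum tolerated dose is reached".

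**The concern.** The second criterion counts days and is blind to quantity. The third looks at quantity, but for one day only and for UX007 only, and its bracketed 25% is not explained. Neither refers to the volume ratio that the SAP itself calls compliance.

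This matters because the product is an oil split over four or more daily doses, and Protocol 7.4.4 reports gastrointestinal limits to tolerability. Partial intake on most days is a foreseeable form of non-adherence, and a day count cannot see it. The Per Protocol analyses of frequency and total duration are the only planned efficacy analyses restricted by dosing adherence. If the Full Analysis Set result were weak, they would be the natural place to ask whether low intake was the reason. As defined, the set may keep the very subjects that the question is about.

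**Working it through.** **Inputs.** Maintenance Period of 8 weeks = 56 days, and a threshold of 80% of days (SAP 6.3). Compliance = ml taken / ml expected × 100 (SAP 8.6.2). The SAP does not define ml expected. Here I assume the full target dose on all 56 days.

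**The plan's own threshold.** 0.80 × 56 = 44.8, so a subject needs 45 of 56 days (45/56 = 80.4%).

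**Dosing patterns**, with amounts as fractions of the daily target:

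| Pattern | Days with a dose | Volume compliance |
|---|---|---|
| A. Quarter dose on 56 days | 56/56 = 100% | (56 × 0.25)/56 = 25.0% |
| B. Quarter dose on 45 days | 45/56 = 80.4% | (45 × 0.25)/56 = 20.1% |
| C. One full-target day, quarter dose on 55 days | 56/56 = 100% | (1 + 55 × 0.25)/56 = 14.75/56 = 26.3% |
| D. One full-target day, quarter dose on 44 days | 45/56 = 80.4% | (1 + 44 × 0.25)/56 = 12/56 = 21.4% |

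All four pass the second criterion. This does not depend on how partial days are treated: a quarter of the volume can be spread over all four daily doses, so that none is missing.

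**Applying the third criterion (UX007 period).** The bracketed 25% has several possible meanings:

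- A quarter of the target: A to D all pass.
- Full target, or within 25% of it: A and B fail, C and D pass.
- A dose equal to 25% of calories, which is 25/30 = 83% of the protocol's target basis: A and B fail, C and D pass.

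So C and D qualify under every reading. Smaller doses on the other days would lower the volume further, since the second criterion has no minimum.

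**Placebo period.** The third criterion names only UX007, so the day count stands alone and all four patterns pass.

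**Effect of a volume rule.** An 80% volume requirement excludes A to D. For a subject who takes either the full dose or nothing, it gives the same cut as the present rule: 45 days is 80.4%, 44 days is 44/56 = 78.6%.

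**Power.** The sample size rests on a difference of 4 events per 4 weeks, an SD of the difference of 7.4, and 40 subjects with 15% discontinuation (SAP 3.6). With 40 × 0.85 = 34 completers, Φ(4/(7.4/√34) − 1.96) = Φ(3.15 − 1.96) = 88%, or about 86% with the t distribution. The stated figure of at least 85% is reproduced, and it does not involve the Per Protocol Set.

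**The case against.** The strongest reply has four parts.

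First, SAP 6.3 and 8.6.2 do not contradict each other. Section 8.6.2 itself lists the day count beside the volume ratio, and 6.3 does not call its criterion compliance. That is correct: this is a weak choice between two measures the SAP already has.

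Second, a reader might infer that a subject who takes a quarter of the dose every day counts as fully adherent. The documents do not support that in general. Such a subject scores 100% on the second criterion, but enters the set only if the bracketed 25% means a quarter of the target. Under the other readings the third criterion keeps the subject out. The reply does not reach patterns C and D, or the placebo period.

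Third, a reader might infer that a recorded dose of zero makes a day count. That is one possible reading; the SAP does not define a non-missing dose.

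Fourth, low intake would not be hidden. SAP 8.6.2 summarises volume compliance, the proportion reaching target and the time to target. SAP 8.6.3 summarises study-drug calories, and Protocol 7.4.7 allows metabolite levels as support. A weak result could be read against these. They are descriptive, however, and do not restrict any efficacy analysis to subjects who took the product.

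**Conclusion.** The point holds in a limited form. The dosing criteria of the Per Protocol Set admit subjects at roughly 21–26% of expected volume even when the one required day is at full target, and at about 20% if the 25% means a quarter of the target. These figures assume that expected volume is the full target on all 56 days. The Per Protocol analyses therefore do not reliably describe the effect in subjects who took the drug.

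A reader might go on to infer a specific dilution of the Per Protocol effect. The documents give no basis for one: they state neither how many subjects would be dosed this way nor how the effect varies with dose. The consequence is confined to two sensitivity analyses. The primary analysis is untouched.

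**What to change.** Replace the second criterion of SAP 6.3 with: dosing compliance as defined in Section 8.6.2 of at least 80% in each of the two planned 8-week Maintenance Periods, for UX007 and placebo alike. In Section 8.6.2, define expected volume, before unblinding, as the volume at the subject's assigned (final titrated) dose recorded in the IWRS. A definition is needed because the protocol allows subjects to remain at a tolerated dose below target.

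Also state whether a recorded 0 ml is a non-missing dose, which still matters for the day count summarised in 8.6.2. Explain the bracketed 25% in the third criterion and reconcile it with the 30% caloric basis in Protocol Table 7.4.4.1.

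The cost is a few lines of SAP text. Daily consumption is already recorded and reconciled with returned bottles (Protocol 7.4.7), and the final titrated dose is already captured (Protocol 8.3). The downsides are:

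- The Per Protocol Set becomes somewhat smaller.
- A subject still titrating after week 2 will score below 100% on those days against the final dose.
- A subject held well below target can still meet the volume criterion, so dose level remains a matter for the third criterion.

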6.4 Safety Analysis Set

The Safety Analysis Set will consist of all enrolled subjects who received at least one dose of investigational product. Subjects will be analyzed according to the actual treatment sequence.

7 DATA SCREENING AND ACCEPTANCE

7.1 General Principles

Data will be reviewed periodically. Any questionable data will be reported to the clinical data manager promptly for query and resolution.

7.2 Handling of Missing and Incomplete Data

Missing clinical outcome data can occur for multiple reasons, including missed subject visits and scales or measures with missing item scores. Missing and incomplete data will be identified for investigation and possible resolution by Data Management prior to the study database lock or snapshot.

Unless specified otherwise, only the observed data will be presented. When a change from baseline is assessed, only patients with a baseline and at least one post-baseline measurement will be included in the analysis.

7.2.1 Missing Date Imputation for Medical History

- If only day is missing, impute as 1.
- If month is missing, impute as January 1st.
- If year is missing, then no imputation will be done and the date will be missing.

If the imputed date is earlier than the birth date, then the birth date will be used.

7.2.2 Missing Date Imputation for AEs and Concomitant Medications

The following conventions will be used to impute missing portions of dates for AEs and concomitant medications. Note that the imputed values outlined here may not always provide the most conservative date.

Missing Start Dates

- If the day is unknown, then:
 - If the month and year match the start date month and year of the first dose of investigational product in this study, then impute as the day of the first dose date.
 - Otherwise, assign the first day of the month.
- If the month is unknown, then:
 - If the year matches the start date year of the first dose of investigational product date in this study, then impute as the month and day of the first dose date in this study.
 - Otherwise, assign 'January'.

- If the year is unknown, then the date will not be imputed and will be assigned a missing value.

If the imputed date is earlier than birth date, then birth date will be used. If the imputed start date is later than the end date, then the start date will be set as the same date as the end date.

Missing Stop Dates and Not Ongoing

- If the day is unknown, then assign the last day of the month.
- If the month is unknown, then assign 'December'.
- If the year is unknown, then the date will not be imputed and will be assigned a missing value, and the event will be considered ongoing. If the AE has been recorded as resolved/recovered, all efforts should be made to obtain the date from the Investigator.

If the resulting end date is after the date of study completion/discontinuation/data cutoff, set the imputed end date as close to the date of study completion/discontinuation/data cutoff as possible without overwritten existing information.

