Triheptanoin was studied in 14 Glut1 DS subjects (including 11 pediatric subjects) in a clinical trial sponsored by [name] at the University of Texas, Southwestern. The results of this open-label study suggest clinical activity with triheptanoin in reducing the frequency of absence seizures (Pascual et al. 2014). No patient experienced serious or unexpected adverse events (AE). One patient (7%) discontinued triheptanoin therapy after 3 weeks owing to gastric discomfort. One other patient (7%) experienced significant (10%) weight gain at 2 months that did not lead to discontinuation. This patient did not follow recommended dietary and nutritional advice to decrease extra sources of fat and simple sugars. Two patients (14%) experienced diarrhea and/or digestive discomfort within days of treatment initiation; symptoms resolved by reducing the triheptanoin dose by one-half and gradually increasing the amount to the target levels over several days.

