At the end of the Run-in Period, eligible subjects will be randomized (1:1) to one of two treatment sequences (UX007/placebo or placebo/UX007). At Randomization, subjects will begin a 10-week double-blind Treatment Period I. At the end of Treatment Period I, subjects will discontinue treatment and begin a 2-week washout period to minimize any potential carryover effect. Subjects will crossover to the second, double-blind treatment assignment (placebo to UX007, UX007 to placebo) for an additional 10 weeks during Treatment Period II. Dosing will be initiated in both treatment periods using a 2-week titration schedule until the subject has reached his/her age-related target dose. If a subject has not reached the target dose by the end of the 2-week titration period, dose titration should continue until the maximum tolerated dose is reached. At the end of the blinded crossover period (Week 22), all subjects will have the option of rolling into the Open-Label Extension (OLE) Period, to continue UX007 treatment for up to 3 years or until approval. A safety follow-up phone call will be conducted 30-35 days after the last dose of UX007G-CL301 study drug.

Figure 1 provides a schematic of the study design.

Figure 1: UX007G-CL301 Study Schematic

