8.9.1 Adverse Events

Adverse events will be coded by SOC and PT using the Medical Dictionary for Regulatory Activities (MedDRA). AEs during Run-In period will be summarized.

A treatment emergent adverse event (TEAE) will be considered and assigned to the treatment group (UX007 or Placebo) if the AE (classified by preferred term) start date occurs or worsens in severity on or after the first dose of study drug in the corresponding treatment period and before the first dose of study drug in the next treatment period. For example, an AE will be assigned to the treatment in Treatment Period I if it occurred during the wash out period. An AE that occurs within 30 days after the last dose of study drug in the last treatment period will be assigned to the last treatment period.

The incidence of subjects reporting TEAEs in each treatment and treatment sequence will be tabulated by SOC and PT; by SOC, PT, and severity; and by SOC, PT, and relationship to study drug. If more than one event occurs with the same preferred term for the same subject, the subject will be counted only once for that preferred term using the most severe and most related occurrence for the summarizations by severity and by relationship to the study drug.

The incidence of subjects reporting TEAEs by treatment and treatment period will also be summarized by SOC and PT for each of the following categories:

- All TEAEs
- Treatment related TEAEs
- Grade 3 or 4 TEAEs
- Serious TEAEs
- Serious and related TEAEs
- TEAEs leading to study discontinuation
- TEAEs leading to treatment discontinuation

- TEAEs leading to death

Exposure adjusted TEAE incidence is defined as total number of occurrences of an event summed across all subjects by treatment divided by the total exposure duration. A TEAE which occurred during the wash-out period will be considered and counted into the first treatment period. Exposure adjusted TEAE incidence will be summarize by treatment, and period.

Detailed listings for all AEs, TEAEs, serious TEAEs, AEs leading to study/treatment discontinuation, and death will also be generated.

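### SAP 7.2.2 anchors partial AE start dates only to the study's first dose, so an event starting just after a later period's first dose can be assigned to the previous period

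*SAP*

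**What the plan says.** **Imputation (SAP 7.2.2).** The rule for an unknown start day begins "If the month and year match the start date month and year of the first dose of investigational product in this study", in which case the first-dose day is used. For every other month: "Otherwise, assign the first day of the month". If the month is unknown and the year is that of the first dose, "then impute as the month and day of the first dose date in this study"; in any other year, January is assigned. The section adds a general caution that the imputed date may not be the most conservative one. It does not mention the first dose of Period II or of the extension.

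**Assignment (SAP 8.9.1).** An AE belongs to a treatment if it starts or worsens "on or after the first dose of study drug in the corresponding treatment period". The window closes when dosing in the following period begins. Washout events go backwards: "an AE will be assigned to the treatment in Treatment Period I if it occurred during the wash out period".

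**Design.** Allocation is 1:1 to UX007/placebo or placebo/UX007 (SAP 3.1). Period II starts at Week 12. From Week 22 all subjects in the extension receive UX007 (Protocol Table 2.2).

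**The concern.** The imputation rule suits a parallel-group trial, where one first-dose date separates untreated from treated time. This crossover has a first dose in each period, and SAP 8.9.1 uses each of them to choose the treatment label. Only the first is protected by the imputation rule.

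The error falls on events that begin soon after a switch. That matters because Protocol 5.2.3 reports early gastrointestinal events in an open-label study of 14 subjects with Glut1 DS: "Two patients (14%) experienced diarrhea and/or digestive discomfort within days of treatment initiation". Safety is part of the primary objective. The affected outputs are the AE tables by treatment and by period, and the exposure-adjusted incidence, where an event would move while its exposure time stays in place.

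**Working it through.** The plan gives no figure for this point, so there is nothing to reproduce. The check applies the SAP 7.2.2 date rule and then the SAP 8.9.1 assignment rule.

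**Inputs.** Period II first dose at +84 days (Week 12) and extension first dose at +154 days (Week 22), as planned. Assumptions: first-dose dates spread evenly over the calendar, 1:1 sequences, an equal AE rate per day, equal weight on the two boundaries, and the extension treated as a next treatment period.

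**Example.** First dose 15 January 2018, so Period II starts 9 April and the extension 18 June. An AE that starts on 12 April and is recorded as April 2018 is imputed to 1 April. That precedes 9 April, so it is assigned to Period I. In a placebo/UX007 subject, a UX007 event becomes a placebo event. In a UX007/placebo subject the reverse happens.

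**Share moved, day missing.** Since 84 and 154 days both exceed a month, a later period's first dose is never in the calendar month of the study's first dose. If that later dose is on day d of a month of L days, an event k days later moves when d ≥ 2 and k ≤ L − d. For a window of W days the share is

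Σ (d = 2 to L) min(W, L − d + 1) / (L × W).

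With L = 30:
- W = 7: (23×7 + 6+5+4+3+2+1) / 210 = 182/210 = 86.7%
- W = 14: (16×14 + 13+12+…+1) / 420 = 315/420 = 75.0%
- W = 70: (29+28+…+1) / 2100 = 435/2100 = 20.7%

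Enumerating every first-dose date over three calendar years gives 86.8%, 75.4% and 21.0%. With the month missing, the same enumeration gives 90% for days 0-69. Period I events: 0%.

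**Share that changes treatment.** A move to an earlier period is not always a change of treatment. At the Period II start it is one in both sequences. At the extension start it is one in only one sequence of the two: UX007/placebo if the event goes back one period, placebo/UX007 if it goes back two, as most month-missing extension events do. The average factor is (1 + 1/2)/2 = 0.75.

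| Missing | True onset (days after dose) | Moved to an earlier period | Label changes (× 0.75) |
|---|---|---|---|
| Day | 0-6 | 87% | 65% |
| Day | 0-13 | 75% | 57% |
| Day | 0-69 | 21% | 16% |
| Month | 0-69 | 90% | 68% |

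At the Period II boundary alone, the third column is also the label-change share.

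**Direction at Period II.** Let u and p be the mean numbers of partial-date events per subject in the window on UX007 and placebo, the same in both periods, and m the share moved. Take one subject per sequence. The true difference over Periods I and II is 2(u − p). As tabulated, UX007 has u + (1 − m)u + mp and placebo has p + (1 − m)p + mu, a difference of 2(1 − m)(u − p). UX007's net loss is m(u − p), which is zero when u = p. Otherwise the difference among these events shrinks to 1 − m: 13%, 25% and 79% of its true size for the three day-missing windows.

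**The case against.** **Few dates may be affected.** Every percentage is conditional on a partial date, and the documents do not say how many to expect. AEs are asked about at each visit (Protocol 7.5.4.10), with contacts at Weeks 12, 14, 16, 18 and 22. Incomplete data are queried before lock (SAP 7.2) and resolved with the investigator (Protocol 8.4.2). This stands. It bears hardest on the month-missing figures, since an unknown month is unlikely with contacts this close. SAP 7.2.2 nevertheless exists for the dates that queries leave open.

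**The tables are descriptive.** SAP 8.9 plans no statistical comparisons of safety data, and all AEs are listed. This limits the weight of the point. But treatment attribution is what the by-treatment tables report, and with about 40 subjects a few moved events could alter a preferred-term row.

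**The SAP warns that dates may not be conservative.** A caution does not correct the assignment.

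**The stronger reading: the rule shifts harm from UX007 to placebo.** A reader might infer this from the example and the gastrointestinal history. The documents do not establish it. Under 1:1 allocation the Period II moves run both ways and cancel at equal AE rates. The early gastrointestinal events come from an open-label study, and placebo here is also an oil, with the same dose level and titration (Protocol 7.4.2). The extension boundary would take events from UX007, but only if the extension is a next treatment period, which SAP 8.9.1 does not state.

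**Conclusion.** The mismatch is real, and no other section corrects it: SAP 7.2.2 can date an event before the dose that preceded it, and SAP 8.9.1 then assigns it to the wrong period. For day-missing events this requires onset in the same calendar month as the later period's first dose, with that dose not on the 1st. The Period II problem stands however the extension is read.

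The 87%, 75%, 21% and 90% are shares of partial-date events moved to an earlier period. They are not shares of all AEs, and across both boundaries they are not shares of wrong treatment labels, which are 65%, 57%, 16% and 68% under the stated assumptions.

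The supported conclusion on direction is dilution of any early difference at Period II. A net loss from UX007 arises only if early AEs are more common on UX007, or through the extension boundary. The absolute number of affected events cannot be derived from the documents. The point merits a correction to the SAP but touches no efficacy result or decision rule.

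**What to change.** In SAP 7.2.2, before unblinding:

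1. Compare a partial AE start date with the first dose of every treatment period, and state whether the extension is one for SAP 8.9.1.
2. Where the known month or year contains a later period's first dose, use the AE stop date and the visit at which the AE was first recorded to place it before or after that dose.
3. If that does not settle it, impute to that period's first-dose date.
4. Flag imputed assignments in the AE listing.

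The cost is a few lines of text and programming, with no change to trial conduct. Step 2 is essential. With the anchor alone, the share of day-missing events moved back from the first 14 days of Period II or the extension falls from 75% to 0%, but about 75% of day-missing events from the 2-week washout move forward to the Period II treatment (0% now). For day-missing events in days 0-69, 6% of those in Period I and 21% of those in Period II would also move forward. With the month missing, imputing to the latest first dose in the year would push forward 86% of Period I and 90% of Period II events in days 0-69, so the visit record has to decide those cases. Even with step 2, some washout events with unknown day will be assigned to the Period II treatment.
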